2.1. Study Rationale

Study CVAC is designed to evaluate safety, tolerability, and PK of oral LY3526318 in healthy participants when LY3526318 is administered as a new formulation. In a prior Phase 1 study (CVAA), exposure did not increase beyond that observed at 100 mg, and the concomitant food administration reduced exposure compared to the fasted state.

In this limited SAD study, a crossover design was chosen to limit the variability of PK, especially for the comparison of PK after fed and fasted conditions. Given treatment-emergent adverse events (TEAEs) were mild in the previous SAD and MD (to 14 days) studies, participants should be able to safely tolerate a maximum of 4 single doses with 14 days of washout between dosing periods. Placebo doses are included to assess TEAEs and limit bias. Similarly, given that a Phase 1 study was previously conducted, sentinel dosing is not necessary. In addition, safety and PK will be assessed prior to each dose escalation to mitigate the possibility of more severe adverse events (AEs) and the PK exceeding the mean area under the concentration versus time curve (AUC) of the monkey NOAEL.

2.2. Background

Chronic pain is a major health issue affecting the quality of life of millions of patients. Nonsteroidal anti-inflammatory drugs are the primary choice of drugs for chronic pain treatment; however, efficacy is limited in many patients. Opioids are potent but sedating and have addictive potential, relegating them to third- and fourth-line treatment options in chronic pain (Ko et al. 2019).

The role of TRPA1 in pain and inflammation and its localization in sensory neurons have been characterized (Bodkin and Brain 2011; Ückert et al. 2017). It evokes pain and an adverse response when administered exogenously (Berta et al. 2017; Demartini et al. 2017; Maatuf et al. 2019; Wang et al. 2019). Additionally, there is genetic evidence for the contribution of TRPA1 to chronic pain.

Transient receptor protein ankyrin-1 antagonists are undergoing evaluation in clinical trials, where there is evidence of efficacy and safety (ODM-108, NCT02432664 [NIH 2017]; GRC 17536; EU Clinical Trial Register 2012-002320-33 [WWW]).

Two Phase 1 studies (CVAA and J2D-MC-CVAB [CVAB]) were conducted to assess tolerability and PK and to assess target engagement, respectively. Study CVAA included a SAD portion, a 2-week multiple ascending dose portion achieving maximum doses of 300 and 100 mg, respectively, and a pilot food-effect portion. Study CVAB assessed target engagement by measuring changes to dermal blood flow following a randomized sequence of 4-single doses: 10 mg, 30 mg, 100 mg, and placebo. There were no clinically significant adverse effects in either of these studies.

In the SAD, plasma exposure increased with increasing doses up to 100 mg, but exposure did not increase at doses of 200 or 300 mg. The geometric mean terminal elimination half-life ($t_{1/2}$) ranged from 9.72 hours to 13.5 hours without an apparent effect of dose over the range of 10 mg

to 300 mg. In addition, when a meal was consumed 30 minutes prior to a 100-mg dose, exposure was approximately 11% of that observed when participants fasted for at least 8 hours prior to and 4 hours after dosing. The new formulation being administered in the current study was developed to increase absorption and to decrease the impact of food.

2.3. Benefit/Risk Assessment

There is no benefit anticipated for healthy participants administered LY3526318.

The current study will be conducted in accordance with principles outlined in the “Guideline on Strategies to Identify and Mitigate Risks for First-in-Human and Early Clinical Trials with Investigational Medicinal Products” (EMA 2017). In Study CVAA, no clinically significant safety or tolerability concerns were identified at the highest single dose administered (300 mg) or the highest multiple dose administered (100 mg once daily for 14 days). Because of the male-only AE observed in rats (seminiferous tubule degeneration), dosing in CVAA was limited to 100 mg for males, with higher doses being administered to females only. This effect was not observed in 2 subsequent male rat studies and was not observed in a 1-month monkey toxicology study, so males will be enrolled in the current study. As described in Section 4.3, subsequent dose regimens will be selected to maintain exposure below the nonclinical NOAEL exposure.

In a biomarker study (Study CVAB), there was evidence of target engagement at 3 hours, but not 24 hours after a single dose of 100 mg. Regarding the current study that uses a new formulation of LY3526318, exposure following the proposed initial dose of 100 mg is projected to be similar to or slightly greater than the exposure achieved in the prior study.

The benefit-risk for the participants treated with LY3526318 remains unchanged in relation to the coronavirus disease 2019 (COVID-19) pandemic as currently based on the results from clinical and nonclinical data. There is no evidence that administration of LY3526318 will lead to suppression or modulation of the immune system. In addition, the mode of action does not appear to have a substantial effect on the respiratory or cardiovascular system critically affected by a severe acute respiratory syndrome coronavirus 2 (SARS-CoV-2) infection. As the participants to be included in this study are generally young to middle aged and healthy (without major comorbidities), the study population is not considered to be a high-risk population for serious COVID-19 disease. Only persons with a negative SARS-CoV-2 test at admission to the CRU will be allowed to participate in the study. In addition, all appropriate measures to prevent SARS-CoV-2 infection during the study will be taken as detailed in site standard operating procedures (SOPs).

More detailed information about the known and expected benefits and risks and reasonably expected AEs of LY3526318 may be found in the Investigator’s Brochure (IB).

3. Objectives and Endpoints

Objectives	Endpoints
Primary (Part A – SAD)	

 To determine the pharmacokinetics of LY3526318 after a single oral dose administration 	
 AUC C_{max}
Primary (Part B – MD)	

 To determine the pharmacokinetics of LY3526318 after multiple oral dose administrations 	
 AUC C_{max}
Secondary (Part A – SAD)	

 To estimate the safety and tolerability of LY3526318 after single (Part A) oral administration to healthy participants To evaluate the effect of a meal on the pharmacokinetics of LY3526318 in fed versus fasted conditions 	
 AEs SAEs C_{max} t_{max} AUC
Secondary (Part B – MD)	

 To estimate the safety and tolerability of LY3526318 after multiple oral administrations to healthy participants 	
 AEs SAEs

Abbreviations: AE = adverse event; AUC = area under the drug concentration versus time curve; C_{max} = maximum observed drug concentration; MD = multiple dose; SAD = single-ascending dose; SAE = serious adverse event.

4. Study Design

4.1. Overall Design

This is a Phase 1, SAD (Part A) and MD (Part B) study of LY3526318 in healthy participants. Both parts are randomized, double-blind, and placebo-controlled. A maximum of 16 participants (SAD and MD cohorts of size 8, randomized 3:1) will be randomly assigned to study intervention such that approximately 16 evaluable participants complete the study.

Part A (SAD):

Single-ascending doses of LY3526318 or placebo will be administered under fasted conditions, beginning with a dose of 100 mg in a cohort of 8 participants. Up to 3 dose levels in a cohort of participants will be administered in a fasted state (fasted for at least 8 hours prior to dosing and for at least 4 hours after dosing). The dose escalation may be stopped if a projected dose may exceed the toxicology NOAEL. Each dose will be separated by at least 1 week. The initial single dose level is the equivalent of 100-mg original formulation, the dose that produced maximum $AUC_{0-\infty}$ ($56 \mu\text{g}\cdot\text{h}/\text{mL}$) in Study CVAA. This dose level was selected because it produced the highest exposure when administered using the original formulation of LY3526318, and if the new formulation produces the maximum theoretical exposure increase of 2-fold compared to the prior study, a 2-fold exposure increase is considered safe and appropriate. Up to 2 additional single dose levels may be administered in a fasted state and these doses would be selected to maintain human $AUC_{0-\infty}$ below the lowest animal-toxicology NOAEL ($154 \mu\text{g}\cdot\text{h}/\text{mL}$, established in a 1-month monkey study).

Doses that were administered in a fasted state may also be administered in a fed state to determine if food decreases exposure when LY3526318 is administered in the new formulation. For the fed state, a standardized, high-fat meal or a light breakfast (as described in site-specific manual) will be consumed prior to dosing. Approximately 50% of the total caloric content of the high-fat meal should be from fat. Study participants should eat this meal in 30 minutes or less, and the study intervention should be administered 30 minutes after the start of the meal. In all cases, study intervention should be taken with 1 glass (approximately 240 mL) of water, and no food should be allowed for at least 4 hours post dose. Water can be allowed as desired except for 1 hour before and after drug administration.

Following a screening period of up to 28 days, eligible participants will be confined to the CRU from Day -1 until all study assessments are completed on Day 3. All participants will return to the CRU after the last study period for a final visit on Study Day 10.

Part B (MD):

After a dose is identified from Part A, multiple doses of LY3526318 or placebo will be administered for up to 5 days. Additional participants will be enrolled for a total cohort size of 8 completers. The assignment to placebo or LY3526318 treatment will be determined at initial randomization to a treatment sequence.

Participants will be confined to the CRU from Day -1 until all study assessments are completed 72 hours after the last dose. Participants will begin receiving multiple once-daily doses of LY3526318 following a review of safety and PK data from Part A, and dose levels will not

exceed those administered in Part A. After review of the data from Part A, Part B doses may be administered in a fed or fasted state or either on different days.

Participants will return to the CRU for a final visit on approximately Day 14.

Safety, PK, and other assessments will be performed at time points, as prescribed in Section 1.3, during the stay at the CRU and at subsequent study visits in Part A and Part B.

Study governance considerations are described in detail in Section 10.1, Appendix 1.

4.2. Scientific Rationale for Study Design

In Study CVAA, all single doses and MDs were well tolerated, but exposure did not increase at doses above 100 mg. In addition, consumption of a meal was found to significantly decrease exposure compared to when participants fasted. This study will include dose escalation beginning with approximately 100 mg, the dose level associated with the highest exposure in the CVAA study, and will include an assessment of food effect. Residual exposure will be minimized due to a washout period of at least 1 week between doses. The PK sampling schedule is designed to measure LY3526318 concentrations over at least 5 half-lives.

Part B is a repeat-dose phase designed to assess tolerability and exposure with repeated doses.

4.3. Justification for Dose

In a prior Phase 1 study (CVAA), there were no clinically significant adverse events at the highest doses administered: 300 mg in the SAD and 100 mg/day for 14 days in the MD. These doses were administered to females only, but there was no apparent difference in exposure or tolerability at lower doses administered to males and females. 100 mg/day was selected as the highest dose for the MD, because plasma exposure did not increase with increasing dose beyond 100 mg. In addition, when a meal was consumed 30 minutes prior to a 100 mg dose, exposure was approximately 11% of that observed when participants fasted. The new formulation being administered in the current study was developed to increase absorption and to decrease the impact of food. The current formulation could produce exposures up to 2.5 times those of the prior form for any given dose level.

The NOAEL from Good Laboratory Practice toxicology studies was established in a 1-month monkey study (Study 00926044). There were no adverse effects in monkeys administered 1000 mg/kg/day, and the mean AUC₀₋₂₄ was 154 $\mu\text{g}\cdot\text{h}/\text{mL}$. As summarized in Table 4.1, in the clinical study, CVAA, a dose of 100 mg resulted in a mean AUC_{0-inf} of 56 $\mu\text{g}\cdot\text{h}/\text{mL}$, and this is planned to be the starting dose in CVAC. The planned maximum dose of 275 mg is based on an assumption of a dose-proportional increase in exposure. The determinant of the maximum dose will be the NOAEL AUC of 154 $\mu\text{g}\cdot\text{h}/\text{mL}$. In the event that a less-than-dose-proportional increase in exposure is observed, a unit dose higher than 275 mg may be used, as long as a mean AUC of 154 $\mu\text{g}\cdot\text{h}/\text{mL}$ is not exceeded. As a practical limit, the unit dose will not be more than 1000 mg. In addition, if a dose lower than 100 mg is needed to maintain AUC < 154 $\mu\text{g}\cdot\text{h}/\text{mL}$, de-escalation is permitted. For the multiple-dose portion of the study, the dose regimen and fed/fasting will be selected with the intent not to exceed the AUC₀₋₂₄ achieved in Part A.

Table 4.1. Margin of Safety for Oral Administration of LY3526318 Based on Administered Dose and Exposure

	Dose (mg/kg)	Dose (mg/m ²)	Dose Multiple ^a	AUC ($\mu\text{g}\cdot\text{h}/\text{mL}$) ^a	Exposure Multiple ^b
Human					
Starting dose (100 mg)	1.67	61.7		56	
Maximum dose (275 mg) ^c	4.6	170		154	
Rat NOAEL^d					
Male	1000	6000	97 ^e 35 ^f	131	2.3 ^e 0.85 ^f
Female	1000	6000	97 ^e 35 ^f	295	5.3 ^e 1.9 ^f
Monkey NOAEL^g	1000	12000	194 ^e 71 ^f	154	2.8 ^e 1 ^f

Abbreviations: AUC = area under the concentration versus time curve; AUC_{0-inf} = area under the concentration versus time curve from time zero to infinity; AUC_τ = area under the concentration versus time curve during a dosing interval; NOAEL = no-observed-adverse-effect level.

- ^a AUC for humans is AUC_{0-inf} after a single dose. AUC for rat and monkey is AUC_τ after multiple doses.
- ^b Dose multiple is the dose in animals/dose in humans based on mg/m². Exposure multiple is the calculated AUC in animals/observed or predicted AUC in humans.
- ^c The planned maximum dose of 275 mg is based on an assumption of dose-proportional increase in exposure. The determinant of the maximum dose will be the NOAEL AUC of 154 $\mu\text{g}\cdot\text{h}/\text{mL}$. In the event that a less-than-dose-proportional increase in exposure is observed, a unit dose higher than 275 mg may be used, as long as a mean AUC of 154 $\mu\text{g}\cdot\text{h}/\text{mL}$ is never exceeded. As a practical limit, the unit dose will not be more than 1000 mg.
- ^d NOAELs from the 4-week, repeat-dose toxicity study (Study # 00926043).
- ^e Based on human exposure at 100 mg using the prior formulation (Study CVAA).
- ^f Based on the highest projected exposure (NOAEL of 154 $\mu\text{g}\cdot\text{h}/\text{mL}$) at a 275 mg dose using the new formulation.
- ^g NOAEL from the 4-week, repeat-dose toxicity study (Study # 00926044; no LY3526318-related effects were noted).

4.4. End of Study Definition

End of the study is the date of the last visit or last scheduled procedure shown in the SoA (Section 1.3) for the last participant.

5. Study Population

Eligibility of participants for the study will be based on the investigator's judgment on results of screening medical history, physical examination, vital signs, clinical laboratory tests, and electrocardiogram (ECG). The nature of any conditions present at the time of the physical examination and any pre-existing conditions will be documented.

Screening may occur up to 28 days prior to enrollment.

Prospective approval of protocol deviations to recruitment and enrollment criteria, also known as protocol waivers or exemptions, is not permitted.

5.1. Inclusion Criteria

Participants are eligible for inclusion in the study only if they meet all of the following criteria at screening. The timeframes included in the following criteria are relative to screening unless otherwise noted.

Age

1. Aged 18 to 65 years, inclusive.

Sex

2. Healthy male participants, as determined through medical history and physical examination.
 - a. A nonvasectomized, male participant must agree to use a condom or abstain from sexual intercourse from start of dosing until 105 days beyond the last dose of study intervention.
 - b. No restrictions are required for a vasectomized male provided his vasectomy has been performed at least 4 months or prior to screening. A male who has been vasectomized <4 months prior to screening must follow the same restrictions as a nonvasectomized male
 - c. Must agree not to donate sperm from start of dosing until 105 days beyond the last dose of study intervention.
3. Healthy female participants of child-bearing potential who have a fertile male sexual partner must be willing and able to practice effective contraception from admission to 105 days beyond the last dose of study intervention. Sexually active participants must use a combination of 2 of the following methods of contraception, including at least 1 so-called 'barrier' method:
 - a. hormonal contraceptives (oral, transdermal patches, vaginal, or injectable)
 - b. intrauterine device with or without hormones
 - c. condom, diaphragm, or cervical cap ('barrier' method), and
 - d. sexual abstinence.

Contraceptive requirements do not apply for participants who are exclusively in a same-sex relationship. Additional guidance is provided in Section [10.4](#), Appendix 4.

Weight

4. Have a body mass index of 18 to 32 kg/m², inclusive.

Type of Participant and Disease Characteristics

5. Are reliable and willing to make themselves available for the duration of the study and are willing to follow CRU-specific study procedures.
6. Have clinical laboratory test results within normal reference range for the population or CRU, or results with acceptable deviations that are judged not clinically significant by the investigator.

Informed Consent

7. Capable of giving signed informed consent as described in Section [10.1.2](#), Appendix 1, which includes compliance with the requirements and restrictions listed in the informed consent form (ICF) and in this protocol.

5.2. Exclusion Criteria

Participants are excluded from the study if they meet any of the following criteria at screening, unless otherwise noted:

Medical Conditions

1. Have a history or presence of medical illness including, but not limited to, any cardiovascular, hepatic, respiratory, hematological, endocrine, psychiatric or neurological disease, convulsions, or any clinically significant laboratory abnormality that, in the judgment of the investigator, indicate a medical problem that would preclude study participation.
2. Any abnormalities identified following a physical examination of the participant that, in the opinion of the investigator, would jeopardize the safety of the participant or interfere with study conduct if they took part in the study.
3. Positive SARS-CoV-2 virus nasopharyngeal polymerase chain reaction test at Day -1.
4. Contact with SARS-CoV-2-positive or COVID-19 patient within the last 14 days prior to admission to the CRU.
5. In the opinion of the investigator, are considered to be a danger to themselves or who have answered “yes” to either Question 4 or Question 5 on Suicidal Ideation portion of the Columbia-Suicide Severity Rating Scale (C-SSRS); or answered yes to any of the suicide-related behaviors on the Suicidal Behavior portion of C-SSRS; and the ideation and behavior occurred within the past 6 months.

6. Have an abnormality in the 12-lead ECG that, in the opinion of the investigator, increases the risks associated with participating in the study. In addition, participants with the following findings will be excluded:
 - a. Confirmed Fridericia's corrected QT (QTcF) interval >450 msec for men and >470 msec for women; one repeat ECG may be performed if required.
7. Have a history of clinically significant multiple or severe drug allergies or severe posttreatment hypersensitivity reactions, which in the opinion of the investigator, may hamper participation in the study.
8. Show evidence of human immunodeficiency virus (HIV) and/or positive human HIV antibodies, hepatitis C and/or positive hepatitis C antibody, or hepatitis B and/or positive hepatitis B surface antigen.
9. Have an abnormal blood pressure (supine) defined as a diastolic blood pressure >90 or <45 mmHg and/or a systolic blood pressure >160 or <90 mmHg. Retesting may occur once during the screening visit within 2 hours of the initial abnormal blood pressure measurement at the discretion of the investigator.

Prior/Concomitant Therapy

10. Have received treatment with biologic agents (such as monoclonal antibodies, including marketed drugs) within 3 months or 5 half-lives (whichever is longer) prior to dosing.
11. Are unwilling to stop herbal supplements, over the counter, or prescription medicines, including drugs that are known inducers or inhibitors of CYP3A4 or 2C9 (see Section 10.6, Appendix 6, for a list of excluded medications), within 14 days prior to study intervention administration and for duration of study. An exception is for paracetamol at doses of ≤ 2 grams/day.

Prior/Concurrent Clinical Study Experience

12. Are currently enrolled in a clinical drug study or are within 30 days prior to (the first) drug administration or in more than 4 other drug studies in the 12 months prior to (the first) drug administration involving an investigational product or any other type of medical research judged not to be scientifically or medically compatible with this study.
13. Have previously completed or withdrawn from this study or any other study investigating this study intervention.

Other Exclusions

14. Participants with a history of drug abuse which, in the opinion of the investigator, is clinically significant or who test positive for drugs of abuse at screening or admission.
15. Have an average weekly alcohol intake that exceeds 21 units per males and 14 units for females per week (1 unit = 12 oz or 360 mL of beer; 5 oz or 150 mL of wine; 1.5 oz or 45 mL of distilled spirits).

16. Are unwilling to stop alcohol and caffeinated beverage consumption and smoking/use of tobacco while resident in the CRU.
17. Are unwilling to comply with the dietary restrictions required for this study, including the avoidance of, by 5 days prior to study intervention administration until the final ambulatory visit, the ingestion of fruits, sauces, and juices containing furanocoumarins that irreversibly inhibit CYP3A4. The following fruits, sauces, and juices are excluded: grapefruit, Seville oranges, pomelos, cranberries, Goji berries, and apples.
18. Are unable to successfully complete a capsule swallow test, which may be performed at screening for any participant assigned to a dose level where more than 3 capsules will be administered.
19. Have donated blood of more than 450 mL within 60 days prior to (the first) drug administration.
20. Are the investigator or CRU personnel directly affiliated with this study or are immediate family members of the investigator or CRU personnel. Immediate family is defined as a spouse, parent, child, or sibling, whether biological or legally adopted.
21. Are Eli Lilly and Company (Lilly) employees or contractors or an immediate family member of employees or contractors.

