9.1. Statistical Hypotheses

No formal hypothesis testing will occur. Exposure, safety, and tolerability endpoints will be summarized for the SAD and MD portions descriptively by dose and fed status and also provided in patient listings.

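### Exclusion 5 lists its suicide-risk triggers as alternatives but closes with a time clause that, read literally, needs both recent ideation and recent behavior

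*Protocol*

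**What the plan says.** Protocol 5.2 introduces its list with "Participants are excluded from the study if they meet any of the following criteria at screening, unless otherwise noted", so meeting one criterion is enough. Criterion 5 has four parts:

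- **Opinion trigger and start of the ideation trigger:** "In the opinion of the investigator, are considered to be a danger to themselves or who have answered" yes to Question 4 or 5 of the C-SSRS ideation section.
- **Behavior trigger:** "or answered yes to any of the suicide-related behaviors on the Suicidal Behavior portion of C-SSRS".
- **Time clause:** "and the ideation and behavior occurred within the past 6 months".

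No other section restates or explains the criterion. The schedules of activities in Protocol 1.3 list the C-SSRS as an assessment at screening, Day -1 and follow-up in both parts. SAP 17.1.8 provides only for listing the results. The opening of Protocol Section 5 says what the eligibility judgment rests on (medical history, physical examination, vital signs, laboratory tests, ECG), does not name the C-SSRS, and rules out waivers of the enrollment criteria.

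**The concern.** The triggers are alternatives, but the condition attached to them is a conjunction. If the conjunction is taken at its word, it cancels the *or* between the two C-SSRS triggers. A candidate who answered yes to Question 5 for last month and reports no behavior would not meet the C-SSRS part of the criterion. Nor would a candidate with a recent suicidal behavior and no Question 4/5 ideation.

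The scope of the clause is a second uncertainty. It may qualify only the C-SSRS triggers, or the whole sentence including the opinion trigger.

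This is an operative safety rule, and the only place in the protocol where a C-SSRS answer has a stated consequence. With waivers barred, the enrollment decision turns on these words, and two screeners could apply them differently to the same answers.

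**Working it through.** There is no design figure to reproduce. Protocol 9.1 states "No formal hypothesis testing will occur", and the point involves no sample size, error rate or endpoint. The check is logical.

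Let A = the investigator judges the candidate a danger to self; I = Question 4/5 ideation within 6 months; B = suicidal behavior within 6 months. Three readings of the criterion:

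1. The clause governs the whole sentence, literal *and*: (A or I or B) and (I and B), which reduces to I and B.
2. The clause governs only the C-SSRS triggers, literal *and*: A or [(I or B) and (I and B)], which reduces to A or (I and B).
3. The clause is distributive, each event needing only to be recent itself: A or I or B.

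| A | I | B | Reading 1 | Reading 2 | Reading 3 |
|---|---|---|---|---|---|
| no | no | no | not excluded | not excluded | not excluded |
| no | no | yes | not excluded | not excluded | excluded |
| no | yes | no | not excluded | not excluded | excluded |
| no | yes | yes | excluded | excluded | excluded |
| yes | no | no | not excluded | excluded | excluded |
| yes | no | yes | not excluded | excluded | excluded |
| yes | yes | no | not excluded | excluded | excluded |
| yes | yes | yes | excluded | excluded | excluded |

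Three things follow.

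- **Candidates not judged a danger.** Three patterns involve a recent event: ideation only, behavior only, both. Both literal readings exclude one of the three; the distributive reading excludes all three.
- **Candidates judged a danger.** Reading 1 fails to exclude three of the four patterns under criterion 5, whereas readings 2 and 3 exclude all four. The scope of the clause therefore matters separately from the choice between *and* and *or*.
- **Redundancy.** Under either literal reading the *or* between the two C-SSRS triggers does no work, because (I or B) and (I and B) is simply I and B.

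A fourth parsing attaches the clause to the behavior trigger alone, so that Question 4/5 ideation would exclude with no time limit. It is less natural, because the clause itself names ideation.

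Usage elsewhere in Protocol 5.2 does not help the distributive reading: criteria 8 and 9 write *and/or* where either element is enough, whereas criterion 5 uses a bare *and*.

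**The case against.** The strongest reply is that the time clause, with its definite article, refers back to the two events just listed, and ordinary English lets such a phrase apply to whichever was reported. The literal reading makes the preceding *or* pointless, and a reader normally avoids an interpretation that empties part of a sentence. This stands: the distributive meaning is plausible and probably intended.

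The second reply is that other text covers much of the gap. A recent yes to Question 5 or a recent behavior bears directly on the opinion trigger. Criterion 1 covers psychiatric disease "that, in the judgment of the investigator, indicate a medical problem that would preclude study participation", and inclusion criteria 2 and 3 ask for healthy participants. This stands in part. The opinion trigger and criterion 1 lower the practical risk, but both rest on the investigator's judgment, and under reading 1 the opinion trigger is itself limited. They do not settle what the C-SSRS triggers mean.

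A reader might go further and infer any of the following, which the documents do not support:

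- *That the protocol admits candidates with recent suicidal ideation or behavior.* The wording permits that result on one reading; the *or* list points the other way, and investigator judgment remains a route to exclusion.
- *That any suicidal ideation is at issue.* The ideation trigger covers Questions 4 and 5 only, on every reading.
- *That the C-SSRS triggers were included to keep exclusion independent of opinion.* No section states their purpose, and they share a sentence with an opinion trigger.
- *That the one-in-three count measures people.* It counts answer patterns.

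**Conclusion.** The point holds as a drafting conflict. The list of triggers and the time clause do not agree, and nothing else in the protocol or SAP reconciles them. Taken literally, the C-SSRS triggers miss two of the three recent-event patterns, leaving those candidates to investigator judgment; whether the opinion trigger is also restricted cannot be determined from the text.

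The practical size is small. At most 16 healthy participants are enrolled (Protocol 1.1), and the documents give no frequency for such answers; that they will be rare is an assumption. That screeners would actually disagree is possible but not shown. The conclusion rests on the wording alone, and the priority is low: worth correcting because it concerns participant safety and the correction is slight.

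**What to change.** Reconcile the *or* list with the *and* time clause in criterion 5 by stating two things:

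1. Whether the 6-month window applies to each C-SSRS trigger separately. If it does, replace the *and* between ideation and behavior in the time clause with *or*. If both events really are required, reword the list of triggers so that it says so.
2. Whether the window applies to the investigator-opinion trigger. The one-word change does not settle this, so it needs its own statement, for example by setting the opinion trigger and the C-SSRS triggers out as separate sub-items.

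The cost is one word and about one sentence of protocol text, plus the ethics committee approval that Protocol 10.1.1 requires for any amendment. No new assessment is needed, since the C-SSRS is already scheduled at screening and Day -1 in both parts, and the SAP needs no change.
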